1.2 Schedule of Assessments

Visits will be conducted as described:

Study Day ¹	Screening	Treatment					Post-Treatment Follow Up		
		1 ²	2	3 ²	4	5 ²	7	28	60
Visit Window (+/- # days)	--	--	--	--	--	--	3	3	3
COVID-19 tests	X								
Informed consent	X								
Medical history and pre-existing conditions	X								
Electrocardiogram (ECG)	X								
Pregnancy test	X								
Inclusion/exclusion criteria	X	X							
Demographics	X								
Randomization		X							
Treatment ^{1,2}		X	X	X	X	X			
Health check ^{1,2}		X		X		X			
Blood oxygen saturation		X					X	X	X
Assessment of 14 Common COVID-19-related symptoms questionnaire		X					X	X	X
Borg Dyspnoea Scale (mBDS)		X					X	X	X
Walk test		X					X	X	X
Chest x-ray imaging		X ³							X
Concomitant medications ²		X	X	X	X	X	X	X	X
Quality-of-Life Assessment SF-36		X					X	X	X
PROMIS Fatigue questionnaire		X					X	X	X
PROMIS Sleep Disturbance questionnaire		X					X	X	X
Adverse events ²		X	X	X	X	X	X	X	X

¹ Day 1, baseline assessments (health check, blood oxygen saturation, assessment of symptoms/questionnaires, mBDS, walk test, and chest x-ray) should occur before the first dose of treatment. These tests and the first dose of treatment will occur at the clinic. Treatment for the remainder of Day 1 and Days 2, 3, 4, 5 will occur at home.

² Day 1 post-first dose, Day 3 and Day 5 health check, concomitant medications and adverse event collection will occur via telephone visit.

³ Baseline chest x-ray may be performed after Screening, up to 3 days prior to Day 1.

TABLE OF CONTENTS

1	PROTOCOL SUMMARY	3
1.1	Protocol Synopsis.....	3
1.2	Schedule of Assessments	8
2	INTRODUCTION	13
2.1	Study Drug	13
2.2	Background to the Disease.....	14
2.3	Previous Human Experience.....	14
2.4	Study Rationale.....	15
2.4.1	Study Design.....	15
2.4.2	Study Background.....	15
2.4.3	Preclinical Data.....	16
2.4.4	Dosing Rationale.....	17
2.5	Benefit and Risk Assessment.....	17
3	STUDY DESIGN.....	18
3.1	Study Design Overview	18
3.2	Study Objectives	18
3.2.1	Primary Objective	18
3.2.2	Secondary Objectives.....	18
3.3	Study Endpoints	18
3.3.1	Primary Endpoint	18
3.3.2	Exploratory Endpoints	18
3.4	Blinding and Randomization	19
3.5	Data Safety Monitoring Board.....	20
3.6	Stopping rules	20
4	SELECTION OF PARTICIPANTS	21
4.1	Number of Participants	21
4.2	Recruitment Methods.....	21
4.3	Participant Characteristics	21
4.4	Inclusion Criteria	21
4.5	Exclusion Criteria	22
5	STUDY PLAN, PROCEDURES, AND ASSESSMENTS	23
5.1	Study Plan	23

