5 STUDY PLAN, PROCEDURES, AND ASSESSMENTS

5.1 Study Plan

Patients with confirmed COVID-19 infection will be screened for up to 72 hours from referral to an outpatient clinic. Patients meeting the selection criteria will be approached for consent in the study. If consented, participants will be randomized in one of two groups, active or control. Within each group, participants are randomized 1:1 following an equal allocation to treatment arms to either active or control arms of the study as follows:

Treatment Arm	Investigational Treatment
Active	Ampion Inhalation for 5-days
Control	Placebo Inhalation for 5-days

Participants who have been randomized into the control arm will receive a daily dose (32mL/day) of placebo (saline) inhalation treatment. Participants who have been randomized into the active treatment arm will receive a daily dose (32mL/day) of inhaled Ampion. Inhaled treatment (Ampion or placebo) will be delivered four times daily, every four to six hours using the nebulizer in equally divided doses of 8mL. This treatment regimen is repeated for 5 days.

The health check vital signs and baseline assessments for blood oxygen saturation, assessment of symptoms/questionnaires, mBDS, walk test, and chest x-ray should occur before the first dose of treatment. These tests and the first dose of treatment will occur at the clinic. Treatment for the remainder of Day 1 and Days 2, 3, 4, 5 will occur at home. Health checks, concomitant medications, and adverse events for Day 1 post-first dose and Days 3 and 5 will be collected via telephone visit.

Safety will be assessed by recording adverse events and with a health check during treatment. Safety is assessed by recording adverse events for the length of the study (60 days).

Efficacy will be assessed by recording the effects of inhalation Ampion compared to placebo on the clinical outcomes for participants with prolonged respiratory complications after a COVID-19 infection using the following clinical outcomes: time to symptom improvement, percentage of participants demonstrating improvement, change in Borg Dyspnoea Scale, time to sustained recovery, blood oxygen saturation, a walk test, and chest x-ray. Assessments for clinical outcomes are performed from baseline to Day 7, Day 28, and Day 60.

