5.2.3 Treatment Period (Day 1 to Day 5)

The following procedures will be performed during the Treatment Period (Day 1 to Day 5):

- Begin inhalation treatment of study intervention (active or placebo) daily within 24 hours of randomization. Subjects will administer inhaled treatment (active or placebo) through nebulization daily as described in [Section 2.1](#).

- Subjects will have a general health check conducted via telephone or text message on Day 1, 3, 5.
- Record concomitant medications/therapies
- Record adverse events

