5.3 Assessment Methods

Demographic Data

Demographic data will be collected: age, gender, race, height and weight, comorbidities.

Health Check

A health check will be conducted at the clinic at baseline to include the measurement of vital signs (i.e., heart rate, blood pressure, respiratory rate, temperature). A general health check will be conducted Day 1 post-first dose, Day 3, and Day 5 via telephone visit.

Blood Oxygen Saturation (SpO2)

SpO2 will be collected at baseline and Days 7, 28, and 60 using a pulse-oxygen measuring device.

Assessment of 14 Common COVID-19-related symptoms questionnaire

The FDA assessment of 14 Common COVID-19- related symptoms questionnaire will be conducted at baseline, Day 7, Day 28, and Day 60 as follows:

Example items For items 1–10, sample item wording could be: “What was the severity of your [insert symptom] at its worst over the last 24 hours?”	Example response options and scoring*
1. Stuffy or runny nose	
2. Sore throat	
3. Shortness of breath (difficulty breathing)	
4. Cough	None = 0
5. Low energy or tiredness	Mild = 1
6. Muscle or body aches	Moderate = 2
7. Headache	Severe = 3
8. Chills or shivering	
9. Feeling hot or feverish	
10. Nausea (feeling like you wanted to throw up)	
11. How many times did you vomit (throw up) in the last 24 hours **	I did not vomit at all = 0 1–2 times = 1 3–4 times = 2 5 or more times = 3

continued

Table 1, continued

12. How many times did you have diarrhea (loose or watery stools) in the last 24 hours ??	I did not have diarrhea at all = 0 1–2 times = 1 3–4 times = 2 5 or more times = 3
13. Rate your sense of smell in the last 24 hours	My sense of smell is THE SAME AS usual = 0 My sense of smell is LESS THAN usual = 1 I have NO sense of smell = 2
14. Rate your sense of taste in the last 24 hours	My sense of taste is THE SAME AS usual = 0 My sense of taste is LESS THAN usual = 1 I have NO sense of taste = 2

* Note: Score values are included in the table for ease of reference. FDA cautions against including the score values within the response options presented to trial subjects to avoid confusing subjects.

** The response options shown for items 11 and 12 are intended only for use with a 24-hour recall period.

Time to Sustained Recovery

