6 DISCONTINUATION CRITERIA

6.1 Early Discontinuation of the Study

Discontinuation or temporary suspension is allowed for any reason. The Sponsor may suspend or terminate the study due to the development of any new or unexpected life threatening or adverse events, prolonged hospitalization, or other potential grounds for stopping the study. The number of subjects, as well as the types and the grade severity of the adverse events (according to Common Terminology Criteria for Adverse Events (CTCAE)) may trigger the temporary suspension of study product administration pending a safety investigation as follows:

If any nebulization reactions of grade 3 and above (as defined using the CTCAE grading scale version 5.0 or newer) are observed in any patient within 24 hours of product administration, a safety investigation will occur, which may trigger the temporary suspension of study product administration.

It is agreed that for reasonable cause, either the investigator or the Sponsor may terminate this study, provided written notice is submitted at a reasonable time in advance of intended termination; if by the investigator notice is to be submitted to Ampio Pharmaceuticals, Inc., and if by the Sponsor, notice will be provided to each investigator.

If a severe local reaction or drug-related SAE occurs at any time during the study, the DSMB will review the case immediately.

The study will be immediately suspended and no additional Ampion treatments administered pending review and discussion of all appropriate study data by the DSMB if one or more participants develop any of the following adverse events deemed to be possibly, probably, or definitely related to Ampion by the Investigator and/or Medical Monitor, based upon close temporal relationship or other factors:

- Death
- Respiratory deterioration requiring extracorporeal membrane oxygenation (ECMO)
- Anaphylaxis
- Acute adverse reaction at administration of treatment (i.e., sudden change in vital signs)

The study will not be restarted until all parties have agreed to the course of action to be taken and the IRB/EC has been notified.

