7.1 Dosing and Administration of Study Medication

Study treatment (Ampion or placebo) will be provided as a solution in vials ready for human use and treatment administration. The participant will be trained to self-administer the study treatment. Treatment should start within 24 hours of randomization and should terminate on last treatment day (Day 5).

Study treatment (Ampion or placebo) will be delivered by inhalation using a nebulizer as a 32mL daily dose administered four times daily (8mL per treatment) every four to six hours for five days.

Study treatment (Ampion or placebo) is presented as a sterile liquid in a glass vial. For each use, the contents of are transferred to the drug reservoir in the nebulizer and nebulized continuously until the drug is fully administered.

Study treatment (Ampion or placebo) is aerosolized for inhalation using the Aerogen Ultra handheld nebulizer (Aerogen Limited, Galway, Ireland, FDA 510K K133360), which consists of the Aerogen Pro-X Controller and the Aerogen Ultra handheld unit. The system is a portable medical device for single patient use indicated for aerosolization of physician-prescribed solutions for inhalation. Ampion is nebulized using the continuous setting on the Aerogen controller, and the study drug is nebulized until it is fully aerosolized.

Product administration may be temporarily suspended until resolution if a serious, or sudden side effects are observed. The nature of the event will be evaluated (i.e., allergic; localized; systemic or otherwise) and appropriate measures applied, which may include symptomatic treatment with antihistamines and antiallergic measures, paracetamol (acetaminophen) and/or corticosteroids.

As described in [Section 6.1](#), if any reactions of grade 3 and above (as defined using the CTCAE grading scale version 5.0 or newer) are observed in any patient within 24 hours of product administration, a safety investigation will occur, which may trigger the temporary suspension of study product administration.

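### Vital signs are scheduled only before the first dose, so four of the SAP's five vital-sign change tables have no scheduled post-baseline value and no scheduled reading follows any dose on Days 1 to 5

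*Protocol*

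**What the plan says.** Protocol 5.1 puts the health-check vital signs and the other baseline assessments ahead of the first dose and adds: "These tests and the first dose of treatment will occur at the clinic". The remaining doses are taken at home. Protocol 5.3 says what the clinic check contains: "A health check will be conducted at the clinic at baseline to include the measurement of vital signs", namely heart rate, blood pressure, respiratory rate and temperature. Protocol 5.2.2 also lists vital signs among the pre-treatment procedures.

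After the first dose the checks are remote. Protocol 5.1 says "Health checks, concomitant medications, and adverse events for Day 1 post-first dose and Days 3 and 5 will be collected via telephone visit", and footnote 2 of the schedule in 1.2 agrees: "Day 1 post-first dose, Day 3 and Day 5 health check, concomitant medications and adverse event collection will occur via telephone visit". Protocol 5.3 says "A general health check will be conducted Day 1 post-first dose, Day 3, and Day 5 via telephone visit", and 5.2.3 allows a text instead of a call: "Subjects will have a general health check conducted via telephone or text message on Day 1, 3, 5". None of these names a measurement. The procedure lists for Days 7, 28 and 60 (5.2.4 to 5.2.6) contain no vital signs, and neither schedule (Protocol 1.2, SAP 14) has a vital-signs row. SpO2 is listed at all three visits. The walk test at those visits also yields pulse (Protocol 5.3, SAP 15.3).

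Two parts of the plan look to vital signs after baseline.

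- **SAP.** Section 8 counts vital signs among the safety analyses. Section 8.4 commits to summaries across time points with change from baseline. Section 12.1 lists five such tables, 10.3.10.1 to 10.3.10.5, and the listings include vital signs with out-of-range values flagged.
- **Protocol 6.1.** One of the events that suspends the study, if judged at least possibly related, is described as: "Acute adverse reaction at administration of treatment (i.e., sudden change in vital signs".

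**The concern.** Safety and tolerability is the primary objective (Protocol 3.2.1). The SAP includes vital signs in its safety evaluation, but the visit schedule does not collect what most of those tables need. The programmer would reach table production with baseline values and, for four of the five variables, nothing planned to compare them with.

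The second issue concerns monitoring. One suspension trigger is explained in terms of vital signs, yet no scheduled reading follows any dose on Days 1 to 5. What could be missed is narrow: mild or unfelt acute changes. An unfelt change in blood pressure cannot be reported by telephone. A mild change in breathing may be hard to tell from the illness itself, because entry requires at least two respiratory symptoms scored two or higher (Protocol 4.4). The synopsis describes this as the first at-home study in long-COVID patients. The clinic dose is the one dose the plan places in the clinic, so readings are cheapest there.

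**Working it through.** The plan gives no figure to reproduce here. The check is a count of scheduled measurements against the planned tables.

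**Step 1. Scheduled measurements per participant** (Protocol 1.2, 5.1, 5.2.2 to 5.2.6, 5.3; SAP 14, 15.3).

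| Measure | Before first dose | After dosing, Days 1 to 5 | Days 7, 28, 60 | SAP vital-sign table |
|---|---|---|---|---|
| Pulse | yes | 0 | 3 (walk test only) | 10.3.10.1 |
| Temperature | yes | 0 | 0 | 10.3.10.2 |
| Systolic BP | yes | 0 | 0 | 10.3.10.3 |
| Diastolic BP | yes | 0 | 0 | 10.3.10.4 |
| Respiratory rate | yes | 0 | 0 | 10.3.10.5 |
| SpO2 | yes | 0 | 3 | none (efficacy table 10.2.4) |

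**Step 2. Tables that lack scheduled post-baseline data.** Temperature, systolic BP, diastolic BP and respiratory rate have none, so 4 of 5 tables are affected. For pulse, subtracting the clinic health-check value from a later walk-test value would compare a reading presumably taken at rest with one taken during or at the end of exercise. A like-for-like comparison is possible only by using walk-test readings at every visit, since the walk test is also done at baseline.

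**Step 3. Doses and readings.**
- Doses per participant: 4 per day × 5 days = 20, of which 1 is in the clinic and 20 − 1 = 19 are at home.
- Doses in the study: 20 × 30 participants = 600.
- Clinic doses: 30, of which 15 are Ampion; 30 / 600 = 5%.
- Full vital-sign sets now scheduled: 1 × 30 = 30, all before dosing and 0 after.
- Remote health checks after dosing starts: 3 per participant (Days 1, 3 and 5), with no measurement specified.

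**Step 4. Effect of the fix.**
- Added sets: 2 after the clinic dose + 1 at Day 7 = 3 per participant; 3 × 30 = 90, of which 60 are post-dose and 30 are on Day 7.
- Total sets: 30 + 90 = 120, or 4 per participant.

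**Step 5. The 6.1 trigger.** The rule turns on relatedness as judged by the investigator or medical monitor, using timing or other factors. It does not require a scheduled reading. Section 7.1 covers pausing treatment: "Product administration may be temporarily suspended until resolution if a serious, or sudden side effects are observed". It then says the event will be evaluated, without saying that vital signs will be taken. Neither document describes a device for measuring vital signs at home. For the 19 home doses the trigger therefore depends in practice on what the participant reports.

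**The case against.** The sponsor has a fair reply. The primary endpoint is the incidence and severity of adverse events, not vital signs. Protocol 5.1 assesses safety through adverse events and a health check, and the protocol's statistical section promises no vital-sign change analysis. The SAP introduction says that not every table will reach the study report, so dropping the tables would remove the mismatch. Expected risk is also modest. The protocol cites an inhaled Phase I study (27 subjects to date), an IV study (10 subjects), more than 1,000 patients given the drug by local injection, and a 5-day inhalation toxicity study with a no-effect level about 15 times the clinical dose.

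Most of this stands, and it limits the point. It does not remove it: SAP 8.4 is a commitment in the text as well as a list of table shells, and the earlier inhaled study was in severe COVID-19. Deleting the tables would settle the mismatch but leave no routine full vital-sign set after any dose.

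Three stronger readings are tempting, and the documents do not support them.

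- **That acute reactions would go undetected, or that the 6.1 rule cannot operate.** The rule is a clinical judgment. Grade 3 or higher reactions within 24 hours, anaphylaxis, death and respiratory deterioration requiring ECMO have their own provisions, and adverse events are collected throughout.
- **That SpO2 is never measured after the first dose.** It is scheduled at Days 7, 28 and 60.
- **That the tables would have no data at all.** Baseline values are scheduled for all five, and unscheduled readings could be added.

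Nothing in either document requires post-dose observation. Adding it is a recommendation. The mismatch between SAP and schedule is a matter of fact.

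**Conclusion.** The point holds and should be fixed. A stated SAP analysis cannot be produced as planned from scheduled data for 4 of 5 tables, and the fifth would mix unlike pulse readings unless it is redefined. On Days 1 to 5 no vital signs, SpO2 or observation period is scheduled after any of a participant's 20 doses, although the first is given in the clinic.

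The size is limited to counts from the documents: 1 scheduled set per participant, 0 after dosing, 4 of 5 tables. The documents give neither a reaction rate nor the variability of vital signs, so no detection probability or precision is claimed. The conclusion assumes that the health check on Days 1 (post-dose), 3 and 5 contains no measurement, as its remote format and the absence of any home device suggest. The primary adverse-event endpoint can still be collected as planned.

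**What to change.** 1. Take vital signs and SpO2 at the end of the Day 1 clinic nebulization and again before discharge, after a short observation period set by the medical monitor.
2. Add vital signs to the existing Day 7 visit; Days 28 and 60 are optional.
3. Enter these time points in Protocol 1.2, SAP 14, SAP 8.4 and tables 10.3.10.1 to 10.3.10.5.
4. Leave the 6.1 rule unchanged. The new readings inform the judgment and do not suspend the study by themselves.
5. Align Protocol 5.2.3, 7.1 and the visit tables in 1.1 and 5.2 with 5.1, so that all say the first dose is given in the clinic. The visit tables now place Day 1 to 5 treatment at home.

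The cost is about 90 short measurement sets, up to about an hour more in the clinic on Day 1, eCRF fields and wording changes, with no added visits. The post-dose readings cover only the clinic dose (30 of 600 doses, 5%); the home doses still depend on participant report.

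If the sponsor declines, remove the four change tables without post-baseline data and amend SAP 8.4 to match. Either drop the pulse change table or base it on walk-test readings at every visit, including baseline.

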5.2 Description of Study Visits

The Schedule of Assessments is shown in [Section 1.2](#). Visit types are described as follows:

Study Day	Visit Description	Visit Type
1	Baseline safety/efficacy measures	Conducted in outpatient clinic
1-5	Ampion inhalation treatment, safety measures	Conducted at home
7, 28, 60	Post-treatment safety/efficacy measures	Conducted in outpatient clinic

5.2.1 Screening (-3 Days to Day 1)

The following procedures will be performed at Screening:

- Evaluate all inclusion and exclusion criteria to ensure that patients meet all inclusion criteria and none of the exclusion criteria.
- Confirm date of initial positive COVID-19 test.
- Medical history, pre-existing conditions, ECG, and comorbidities. Include the symptom onset date for COVID-19 symptoms.
- Obtain informed consent before the starting any study specific procedures, including COVID testing.
- Demographics (age, sex, race, height and weight)
- Pregnancy test for women of childbearing age.

5.2.2 Baseline (Day 1)

The following procedures will be performed at Baseline (first assessment prior to treatment):

- Confirm eligibility (review inclusion/exclusion criteria)
- Randomize patient to study arm. Start inhalation treatment within 24 hours.
- Vital signs
- Blood oxygen saturation
- Assessment of 14 Common COVID-19-related symptoms questionnaire
- Borg Dyspnoea Scale and walk test
- Chest x-ray imaging
- Record concomitant medications/therapies
- Quality-of-life assessment SF-36
- PROMIS fatigue and PROMIS sleep disturbance questionnaires
- Record adverse events

5.2.3 Treatment Period (Day 1 to Day 5)

The following procedures will be performed during the Treatment Period (Day 1 to Day 5):

- Begin inhalation treatment of study intervention (active or placebo) daily within 24 hours of randomization. Subjects will administer inhaled treatment (active or placebo) through nebulization daily as described in [Section 2.1](#).

- Subjects will have a general health check conducted via telephone or text message on Day 1, 3, 5.
- Record concomitant medications/therapies
- Record adverse events

5.2.4 Post Treatment Follow Up (Day 7)

The following procedures will be performed at Day 7 (endpoint):

- Blood oxygen saturation
- Assessment of 14 Common COVID-19-related symptoms questionnaire
- Borg Dyspnoea Scale and walk test.
- Record concomitant medications/therapies
- Quality-of-life assessment SF-36
- PROMIS fatigue and PROMIS sleep disturbance questionnaires
- Record adverse events

5.2.5 Post-Treatment Follow-Up (Day 28)

The following procedures will be performed at follow-up visits (Day 28):

- Blood oxygen saturation
- Assessment of 14 Common COVID-19-related symptoms questionnaire
- Borg Dyspnoea Scale and walk test
- Concomitant medications/therapies
- Quality-of-life assessment SF-36
- PROMIS fatigue and PROMIS sleep disturbance questionnaires
- Record adverse events

